6.4 Missing Data

Individual missing item in any scale will not be imputed. For the rating scales that consist of more than one item, if any item is missing, then the total and subscale scores will also be handled as missing. For example, if one item of PANSS positive subscale is missing, then the PANSS total score, the PANSS subscale scores, and the PANSS five-factor model scores will be missing.

In computing LOCF, unscheduled visits in the double-blind treatment phase will be used. For example, for the double-blind treatment phase, Week 6 (LOCF) endpoint will be the last observation of the post-baseline data specified in 6.3 A. Unscheduled visits in the open-label treatment phase will not be used for Week 52 (LOCF) endpoint.

In the efficacy analysis on data collected in the double-blind treatment phase, the primary method for handling of missing data will be the MMRM without explicit imputations for missing data. The LOCF method will be used with analysis of covariance (ANCOVA) as additional sensitivity analysis. The final post-baseline data in the double-blind treatment phase (on or after Day 1 and through 7 days after the date of final application of the study drug for the double-blind treatment phase) will be carried forward and will be defined as the Week 6 (LOCF) endpoint.

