### **15.3.8.3 Missing Data**

For the rating scales that consist of more than one item, if any item is missing, then the total and subscale scores will also be handled as missing.

In the efficacy analysis on data collected in the double-blind treatment phase, the primary method for handling of missing data will be the MMRM without explicit imputations for missing data. The LOCF method will be used for an analysis of sensitivity. The final post-baseline data in the double-blind treatment phase will be carried forward and will be defined as the Week 6 (LOCF). The final post-baseline value of the entire study duration will be defined as LOCF endpoint for all subjects.

In the safety analysis, the final post-baseline data in the double-blind treatment phase will be carried forward and will be defined as the Week 6 (LOCF). The final post-baseline value of the entire study duration will be defined as the LOCF endpoint for all subjects.

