3.2 Secondary Efficacy Endpoints

- Mean change in PANSS subscale scores (positive, negative, and general psychopathology) from baseline at Week 6
- Mean change in PANSS five-factor model scores (3) from baseline at Week 6
- Mean change in Clinical Global Impressions – Severity of Illness (CGI-S) score from baseline at Week 6
- Mean change in PANSS total score from the last evaluation before the initial application of DSP-5423P at each visit
- Mean change in PANSS subscales (positive, negative, and general psychopathology) from the last evaluation before the initial application of DSP-5423P at each visit
- Mean change in PANSS five-factor models from the last evaluation before the initial application of DSP-5423P at each visit
- Proportion of subjects who achieve a response, defined as 20% or greater improvement from baseline in PANSS total score at Week 6
- Mean change in CGI-S score from the last evaluation before the initial application of DSP-5423P at each visit
- Time to treatment discontinuation from initial application in the open-label treatment phase

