6.8 Rating Scales

6.8.1 Positive and Negative Syndrome Scale (PANSS)

The PANSS is an interview-based measure of the severity of psychopathology in adults with psychotic disorders. The patient is rated from 1 to 7 on 30 different items across three subscales. A score of 1 indicates absence of symptoms absent while 7 indicates extreme symptoms.

The PANSS total score will be calculated as the score sum of all 30 items, and it ranges from 30 (least severe) to 210 (most severe).

The PANSS positive subscale is defined as the score sum of all 7 items within this subscale. The possible values are 7 (least severe) to 49 (most severe). The 7 items are delusions, conceptual disorganization, hallucinatory behavior, excitement, grandiosity, suspiciousness/persecution, and hostility

The PANSS negative subscale is defined as the score sum of all 7 items within this subscale. The possible values are 7 (least severe) to 49 (most severe). The 7 items are blunted affect, emotional withdrawal, poor rapport, passive/apathetic social withdrawal, difficulty in abstract thinking, lack of spontaneity and flow of conversation, and stereotyped thinking

The PANSS general psychopathology subscale is defined as the score sum of 16 items within this subscale. The possible values range from 16 (least severe) to 112 (most severe). The 16 items are somatic concern, anxiety, guilt feelings, tension, mannerisms and posturing, depression, motor retardation, uncooperativeness, unusual thought content, disorientation, poor attention, lack of judgment and insight, disturbance of volition, poor impulse control, preoccupation, and active social avoidance

Additionally, the PANSS five-factor model will also be considered, which is based on the sum of the following items:

Negative symptoms: Blunted affect, emotional withdrawal, poor rapport, passive/apathetic social withdrawal, lack of spontaneity and flow of conversation, and active social avoidance

Excitement: Excitement, hostility, tension, and poor impulse control

Cognitive disorders: Conceptual disorganization, difficulty in abstract thinking, mannerisms and posturing, disorientation, and poor attention

Positive symptoms: Delusions, grandiosity, suspiciousness/feelings of persecution, and unusual thought content

Anxiety/depression: Hypochondria, anxiety, feelings of guilt, depression, and Preoccupation

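### SAP 6.4's worked example sets PANSS subscale and five-factor scores to missing even when all of their own items were rated

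*SAP*

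**What the plan says.** SAP 6.4 opens with "Individual missing item in any scale will not be imputed". It then gives a general rule, in the same words as protocol 15.3.8.3: "if any item is missing, then the total and subscale scores will also be handled as missing". The SAP alone adds a worked example, in which "if one item of PANSS positive subscale is missing, then the PANSS total score, the PANSS subscale scores, and the PANSS five-factor model scores" all become missing. The protocol section has no example and does not mention the five-factor scores.

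SAP 6.8.1 defines each score by its own items:
- "The PANSS positive subscale is defined as the score sum of all 7 items within this subscale"
- "The PANSS negative subscale is defined as the score sum of all 7 items within this subscale"
- "The PANSS general psychopathology subscale is defined as the score sum of 16 items within this subscale"

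The five factors are also sums of listed items. The positive factor, for instance, is "Delusions, grandiosity, suspiciousness/feelings of persecution, and unusual thought content".

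Both families of scores are secondary endpoints. SAP 3.2 lists "Mean change in PANSS subscale scores (positive, negative, and general psychopathology) from baseline at Week 6" and, next to it, the five-factor scores. Under SAP 7.6.2.1.1, subscales and factors are analysed by MMRM and summarised by visit and at the LOCF endpoint. LOCF ANCOVA is specified for the subscales and CGI-S but not for the factors. SAP 7.6.2.1.3 adds by-visit summaries of both over the DSP-5423P treatment period. No secondary analysis carries an adjusted p-value.

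**The concern.** A blank positive item says nothing about whether the negative subscale, or a factor that does not use that item, was fully rated. Setting those scores to missing removes values that were observed.

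Other rules in the SAP can then put an older or different value in their place:
- **Baseline (SAP 6.3 A(i))** is the latest available value from Screening or Day 1. A blank positive item on Day 1 would push the negative and general subscale baselines back to Screening, although both were complete on Day 1.
- **LOCF (SAP 6.4)** takes the last post-baseline observation. A blank item at the final visit would replace a complete final subscale score with an earlier one.
- **Visit mapping (SAP 6.3 A(iii))** allows an empty visit to be filled from a discontinuation or unscheduled assessment, so a subscale that was rated at the scheduled visit could be taken from another day.

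There is also a clarity problem. The general sentence can be read score by score, but the example does not fit that reading. Two programmers could derive different secondary datasets from the same section.

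**Working it through.** The plan states no figure to reproduce. The check is a count of which scores contain each item, followed by an illustration of scale.

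**Step 1. Subscales.** From SAP 6.8.1, the subscales have 7, 7 and 16 items with no overlap: 7 + 7 + 16 = 30. Each item is in exactly one subscale.

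**Step 2. Factors.** The negative, excitement, cognitive, positive and anxiety/depression factors have 6, 4, 5, 4 and 5 items with no overlap: 6 + 4 + 5 + 4 + 5 = 24. This takes hypochondria in the factor list to be the item called somatic concern in the general subscale. Each of these 24 items is in exactly one factor. The other 30 − 24 = 6 are in none: hallucinatory behavior, stereotyped thinking, motor retardation, uncooperativeness, lack of judgment and insight, and disturbance of volition.

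**Step 3. The SAP's own example: one missing positive-subscale item.**
- Subscales that contain it: 1. Subscales voided as written: 3. Fully rated subscales lost: 3 − 1 = 2.
- Factors that contain it: one for each of six items. Delusions, grandiosity and suspiciousness are in the positive factor, conceptual disorganization is in the cognitive factor, and excitement and hostility are in the excitement factor. Hallucinatory behavior is in no factor.
- Factors voided as written: 5. Fully rated factors lost: 5 − 1 = 4, or 5 − 0 = 5 if the item is hallucinatory behavior.

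**Step 4. Any single item.** If the example is meant to stand for all 30 items, and each is equally likely to be the missing one, the average number of truly incomplete factors is 24/30 = 0.8. The average number of valid factor scores lost is 5 − 0.8 = 4.2.

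**Step 5. Scale, for illustration only.** Assume each item is missing independently with probability q; the documents give no value. A score is lost with probability 1 − (1 − q)^30 under the example as written, and 1 − (1 − q)^k if only its own k items count.

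| Assumed q | Any score, as written | 7-item subscale, own items | 16-item subscale, own items | Factors (4 to 6 items), own items |
|---|---|---|---|---|
| 0.05% | 1.5% | 0.35% | 0.8% | 0.2% to 0.3% |
| 0.1% | 3.0% | 0.7% | 1.6% | 0.4% to 0.6% |
| 1% | 26.0% | 6.8% | 14.9% | 3.9% to 5.9% |

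The first results column is also the loss of the PANSS total, which is the same under both rules.

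**The case against.** The strongest defence is consistency. A rule that voids the whole assessment keeps the total, subscales and factors on the same set of assessments. With an own-items rule, a subject with a blank item on Day 1 could have a Screening baseline for the total and a Day 1 baseline for an unaffected subscale. The same split could arise in visit mapping and in LOCF. The three subscale changes would then not add up to the change in the total. This stands as a real, small downside, so it would be wrong to say that the SAP's rule has no possible rationale or that changing it costs nothing. The SAP does not offer this rationale, however. SAP 7.6.1 also summarises each item score separately, and nothing in 6.4 voids the observed items of an incomplete assessment.

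A second defence is that the wording is merely loose. For the factors this has some force: the example does not name the item, and positive-subscale items are spread over three factors, so the plural may be innocent. It does not work for the subscales. A positive-subscale item belongs to one subscale only, and the plural there has no natural narrower meaning.

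Third, missing items are plausibly rare. Protocol 11.2.1 has a certified rater score all 30 items, and protocol 16.2 has CRFs reviewed for completeness. This stands, and it limits the importance of the point.

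A reader might also infer that the protocol has the same fault. Its general sentence can be read score by score, and it has neither the example nor any mention of factors, so the text does not show that.

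**Conclusion.** As written, the SAP 6.4 example discards fully rated secondary-endpoint scores: two subscales and four or five factors for each visit with one missing positive item. The evidence is firm for the subscales and somewhat less so for the factors. The conclusion rests on the item lists in SAP 6.8.1 and on reading the example's plurals at face value.

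The consequence is limited. The subscale MMRM, LOCF ANCOVA and summaries, and the factor MMRM and summaries, can lose observed values. The loss is per visit, the MMRM still uses the subject's other visits, and the rule is prespecified and the same in every arm.

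Three stronger conclusions are tempting but not supported:
- **Loss in the primary analysis.** The total needs all 30 items under either rule. The primary analysis, mITT membership, responder endpoint and interim analysis all rest on the total and do not change.
- **Loss in a LOCF ANCOVA of the factor scores.** SAP 7.6.2.1.1 does not plan one.
- **A large loss of data.** The 26.0% in the table follows from an assumed 1% rate per item, which nothing in the documents supports. The true amount is unknown and probably small.

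This is a cheap improvement, not a threat to the trial's conclusions.

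**What to change.** Replace the example in SAP 6.4 with a sentence such as: *A total, subscale or factor score is set to missing only if an item belonging to that score (Section 6.8.1) is missing.* Align protocol 15.3.8.3 with it and mention the factor scores there. If the derivations are already locked, state which rule was programmed and how many assessments it affected.

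The drafting cost is one sentence in each document. The analytical cost is that N, the baseline visit or the LOCF visit may occasionally differ between the total and the subscale or factor scores. Subscale changes may then not sum exactly to the total change for those subjects, and a table footnote can say so.

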### As needed

- When the Investigator considers a higher dose of DSP-5423P to be necessary due to insufficient efficacy, the DSP-5423P dose can be increased.
- When the Investigator considers a lower dose of DSP-5423P to be necessary due to the AEs, the DSP-5423P dose can be reduced.

PANSS and CGI-S should be evaluated before the dose adjustment at each unscheduled visit (Section 11.2 Efficacy Assessments, p47). DIEPSS should be evaluated as well as PANSS and CGI-S when the DSP-5423P dose is reduced due to extrapyramidal symptoms (Section 11.3 Safety Assessments, p48).

After the dose adjustment, the Investigator will record the reason for the dose

adjustment in the CRFs. The DSP-5423P dose should not be changed for at least 1 week in principle, after the dose adjustment.

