#### **15.3.8.2 Analysis visits, baseline, and post-baseline measures**

All data will be organized and analyzed according to the scheduled timing as outlined in Table 3 to 5 Schedule of Assessments (p10~13) and according to the visit denoted in the CRFs. Unscheduled visits may be used if scheduled visits are not available, and details will be prespecified in the statistical analysis plan before the interim analysis is performed. The baseline data for statistical analyses will be defined as the last non-missing data on or before Day 1. In analysis for the open-label treatment phase and the DSP-5423P treatment period, the baseline data of the subjects in the Placebo group will be defined as the last non-missing data before the beginning of DSP-5423P application. Post-baseline data for statistical analysis will be defined as the non-missing data on or after Day 1 and through 7 days after the date of final

application of the study drug (excluding baseline). The data collected at the discontinuation visit will be mapped to the next scheduled visit of the actual discontinuation date.

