Assessment and tests	Relative Day	Analysis Visit
PANSS, CGI-S, DIEPSS, C-SSRS, Skin irritation assessment, Body weight, Vital signs	Day 1 to 11	Week 1
	Day 12 to 25	Week 2
	Day 26 to 39	Week 4
	Day 40 or later	Week 6
12-lead ECG, Pharmacokinetic	Day 1 to 11	Week 1
	Day 12 to 25	Week 2
	Day 26 or later	Week 6
Laboratory test	Day 1 to 25	Week 2
	Day 26 or later	Week 6

If more than one unscheduled visits satisfy the condition, the earliest one

Statistical Analysis Plan

Version: 2

Study No. D4904020

will be mapped to the analysis visit

Note: non-missing analysis visits will not be replaced.

B. DSP-5423P treatment period

(i) On-Treatment Baseline analysis visit

(1) 40 and 80 mg group in the double-blind treatment phase

Same as the Baseline analysis visit for the double-blind treatment phase.

(2) Placebo group in the double-blind treatment phase

Defined as the last non-missing data in the double-blind treatment phase including unscheduled visits assessed on or before the On-treatment Day 1.

(ii) Post-baseline data

(1) 40 and 80 mg group in the double-blind treatment phase

Defined as the non-missing data on 'On-treatment Day 1' through 7 days after the final application of DSP-5423P, except for Screening and Day 1 (Baseline) visit.

(2) Placebo group in the double-blind treatment phase

Defined as the non-missing data on a day after 'On-treatment Day 1' through 7 days after the final application of DSP-5423P.

(iii) Post-baseline analysis visit for the 40 and 80 mg group

The post-baseline data will be mapped to post-baseline analysis visits, ie, On-treatment Week 1, 2, 4, 6, 7, 8, 10, 14, 18, 22, 26, 30, 34, 42, 50, and 58 according to the CRF visits as follows. Unscheduled visits of the open-label treatment phase will not be mapped.

(1) Scheduled visits except for the discontinuation visits will be mapped regardless of the actual day of assessment as follows:

CRF Visits	DB W1	DB W2	DB W4	DB W6
Analysis Visits	OnT W1	OnT W2	OnT W4	OnT W6
CRF Visits	OL W1	OL W2	OL W4	OL W8
Analysis Visits	OnT W7	OnT W8	OnT W10	OnT W14
CRF Visits	OL W12	OL W16	OL W20	OL W24
Analysis Visits	OnT W18	OnT W22	OnT W26	OnT W30
CRF Visits	OL W28	OL W36	OL W44	OL W52
Analysis Visits	OnT W34	OnT W42	OnT W50	OnT W58

DB, double-blind; OL, open-label; OnT, on treatment; W, Week

Statistical Analysis Plan

Version: 2

Study No. D4904020

- (2) Discontinuation visits will be mapped to the earliest missing analysis visit based on the relative day of assessment as follows:

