Note: non-missing analysis visits will not be replaced in this step.

- (iv) Post-baseline analysis visit for the placebo group

The post-baseline data will be mapped to post-baseline analysis visits, ie, On Treatment Week 1, 2, 4, 8, 12, 16, 20, 24, 28, 36, 44, and 52 according to the CRF visits as follows. Unscheduled visits of the open-label treatment phase will not be mapped.

- (1) Scheduled visits except for the discontinuation visits will be mapped regardless of the actual day of assessment as follows:

CRF Visits	OL W1	OL W2	OL W4	OL W8
Analysis Visits	OnT W1	OnT W2	OnT W4	OnT W8
CRF Visits	OL W12	OL W16	OL W20	OL W24
Analysis Visits	OnT W12	OnT W16	OnT W20	OnT W24
CRF Visits	OL W28	OL W36	OL W44	OL W52
Analysis Visits	OnT W28	OnT W36	OnT W44	OnT W52

OL, open-label; OnT, on treatment; W, Week

- (2) Discontinuation visits will be mapped to the earliest missing analysis visit based on the relative day of assessment as follows:

Statistical Analysis Plan

Version: 2

Study No. D4904020

- ◇ PANSS, CGI-S, DIEPSS, C-SSRS, Skin irritation assessment,
Body weight, Vital signs

Relative Day	Analysis Visit
OL Day 1 to 11	OnT W1, 2, 4, 8, 12, 16, 20, 24, 28, 36, 44, or 52
OL Day 12 to 25	OnT W2, 4, 8, 12, 16, 20, 24, 28, 36, 44, or 52
OL Day 26 to 49	OnT W4, 8, 12, 16, 20, 24, 28, 36, 44, or 52
OL Day 50 to 77	OnT W8, 12, 16, 20, 24, 28, 36, 44, or 52
OL Day 78 to 105	OnT W12, 16, 20, 24, 28, 36, 44, or 52
OL Day 106 to 133	OnT W16, 20, 24, 28, 36, 44, or 52
OL Day 134 to 161	OnT W20, 24, 28, 36, 44, or 52
OL Day 162 to 189	OnT W24, 28, 36, 44, or 52
OL Day 190 to 238	OnT W28, 36, 44, or 52
OL Day 239 to 294	OnT W36, 44, or 52
OL Day 295 to 350	OnT W44 or 52
OL Day 351 or later	OnT W52

Note: non-missing analysis visits will not be replaced.

- ◇ 12-lead ECG, Laboratory test, Pharmacokinetic

Relative Day	Analysis Visit
OL Day 1 to 49	OnT W4, 12, 20, 28, 36, 44, or 52
OL Day 50 to 105	OnT W12, 20, 28, 36, 44, or 52
OL Day 106 to 161	OnT W 20, 28 36, 44, or 52
OL Day 162 to 238	OnT W28, 36, 44, or 52
OL Day 239 to 294	OnT W36, 44, or 52
OL Day 295 to 350	OnT W44, or 52
OL Day 351 or later	OnT W52

Note: non-missing analysis visits will not be replaced.

C. Open-label treatment phase

For the analysis of open-label treatment phase, analysis visits for all treatment groups are derived using the same algorithm for the placebo group for the DSP-5423P treatment period.

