8 CHANGES IN PLANNED ANALYSES

Not applicable.

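### SAP 6.4 narrows the protocol's LOCF endpoint by barring open-label unscheduled ratings, without declaring it, and SAP 7.7.2 has no DIEPSS table for ratings taken before unscheduled dose reductions for extrapyramidal symptoms

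*SAP*

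**What the plan says.** **LOCF in the protocol.** Section 15.3.8.3 states: "The final post-baseline value of the entire study duration will be defined as LOCF endpoint for all subjects". It gives this definition for efficacy and again for safety. Section 15.3.8.2 counts as post-baseline any non-missing value from Day 1 to 7 days after the final application, baseline excepted. Neither section excludes unscheduled visits from LOCF.

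**LOCF in the SAP.** Section 6.4 treats the two phases differently. For the double-blind phase: "In computing LOCF, unscheduled visits in the double-blind treatment phase will be used". For the open-label phase: "Unscheduled visits in the open-label treatment phase will not be used for Week 52 (LOCF) endpoint". It gives no reason for the difference. Section 8, on changes in planned analyses, reads "Not applicable". Section 7.9 says that the submission analysis covers Visits 101 to 108, with discontinuation and unscheduled visits in that span.

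**Visit mapping.** SAP 6.3 B says, for each treatment group: "Unscheduled visits of the open-label treatment phase will not be mapped". Section 6.3 C carries the same algorithm into the open-label analysis. Protocol 15.3.8.2 is permissive here, "Unscheduled visits may be used if scheduled visits are not available", and leaves the details to the SAP.

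**Ratings at unscheduled visits.** Protocol 10.2 says: "PANSS and CGI-S should be evaluated before the dose adjustment at each unscheduled visit". DIEPSS is added only when the dose is reduced for extrapyramidal symptoms (also protocol 11.3.2).

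**DIEPSS outputs.** SAP 7.7.2 summarises DIEPSS by visit and at the LOCF endpoint. It has no worst-value summary.

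**The concern.** There are two separate problems.

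First, the SAP's open-label LOCF is narrower than the protocol's, and the section meant to record such changes says there are none. A subject who is rated at an unscheduled visit and then lost would be carried forward from an earlier scheduled score. Protocol 10.2 ties as-needed dose changes to insufficient efficacy or adverse events, so the omitted ratings are not a random sample.

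Second, the protocol asks for a DIEPSS score just before an unscheduled reduction for extrapyramidal symptoms, and no DIEPSS table has a place for it. From Open-Week 4 to Open-Week 28 scheduled visits are 4 weeks apart; after that, in Japan, they are 8 weeks apart. By the next scheduled rating the dose may have been cut and an antiparkinson drug started (protocol 10.3.5.1), so the tabulated score can describe the managed state instead of the event.

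Long-term safety and efficacy is a stated secondary objective. DIEPSS change from the last evaluation before DSP-5423P is a named safety endpoint.

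**Working it through.** The plan states no figure that can be reproduced here. The check sets the rules side by side, and the only arithmetic is illustrative.

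**Step 1. Is an open-label unscheduled rating post-baseline?** Yes, if it falls within 7 days of the final application of DSP-5423P. Protocol 15.3.8.2 and SAP 6.3 B(ii) agree and exclude no visit type. Under protocol 15.3.8.3 such a rating can therefore be the LOCF value. Under SAP 6.4 it cannot be the Week 52 (LOCF) value.

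**Step 2. For whom do the two definitions differ?**

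| Last rating inside the 7-day window | Protocol LOCF | SAP LOCF | Same? |
|---|---|---|---|
| Scheduled visit | that rating | that rating | yes |
| Discontinuation visit | that rating | that rating | yes |
| Unscheduled open-label visit, nothing later | that rating | an earlier rating | no |

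The second row holds because discontinuation ratings are due within 5 days of the last application (protocol 13.2), which is inside 7 days, and are retained: "Discontinuation visits will be mapped to the earliest missing analysis visit based on the relative day of assessment as follows". The third row can occur. Loss to follow-up is a listed reason for termination (protocol 13.1), and protocol 13.2 asks for every effort to obtain the discontinuation visit without guaranteeing it.

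**Step 3. Size for PANSS.** Let f be the share of subjects in the third row and d the mean amount by which the omitted score is worse than the one carried forward.

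Shift in LOCF mean = f × d

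- Low: 0.01 × 5 = 0.05 points
- High: 0.10 × 20 = 2.0 points
- Narrower assumption, f = 1% to 5% and d = 10 to 20: 0.01 × 10 = 0.1 to 0.05 × 20 = 1.0 point

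Both f and d are assumptions. The primary analysis is an MMRM of double-blind visits, so its shift is 0. The double-blind LOCF sensitivity analysis already uses unscheduled ratings.

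**Step 4. Can a DIEPSS score taken before an unscheduled reduction reach a DIEPSS table?**

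- By visit: no, because open-label unscheduled visits are not mapped.
- LOCF: no, as far as the bar in SAP 6.4 reaches.
- Worst value: none is planned for DIEPSS.

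Repairing LOCF alone would not close this gap. A subject whose dose is reduced normally stays on treatment and is rated again, so the pre-reduction score is rarely the last one. Elsewhere the SAP does capture such values: sections 7.7.5 (marked laboratory abnormalities) and 7.7.7 (QTc prolongation) count a subject with a qualifying value at any post-baseline time, unscheduled visits included.

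**Step 5. What does Week 52 (LOCF) cover?** The label fits open-label treatment in Japan. Outside Japan that phase ends at Open-Week 28. In the DSP-5423P treatment period the 40 mg and 80 mg groups end at On-treatment Week 34 (outside Japan) or Week 58 (Japan), while the placebo group ends at On-treatment Week 28 or 52. The SAP does not say to which of these endpoints the bar applies.

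**The case against.** The strongest reply is that the outputs affected are descriptive summaries from an open-label, flexible-dose phase with no concurrent control and no hypothesis test. The ratings are listed (SAP 7.6 and 7.7). Extrapyramidal adverse events are tabulated by preferred term, maximum severity and first onset; events leading to dose reduction have their own table (SAP 7.7.1); and antiparkinson use is summarised by treatment duration (SAP 7.4.3). All of this stands, and it limits the importance of the point. It does not supply the DIEPSS score itself, and it does not explain an undeclared change of definition.

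It can also be argued that protocol 15.3.8.2 delegates the handling of unscheduled visits to the SAP. For visit mapping that is right. The wording is permissive, and keeping event-triggered ratings out of by-visit means is a defensible convention. The delegation concerns the use of an unscheduled visit where a scheduled one is unavailable; it does not redefine LOCF, which 15.3.8.3 sets out in its own terms.

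A reader might infer more than the documents support:

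- **That the no-mapping rule contradicts the protocol.** It does not, for the reason just given.
- **That DIEPSS is required before every unscheduled dose change.** It is required only before a reduction for extrapyramidal symptoms.
- **That long-term results leave out the ratings taken whenever a dose failed or was not tolerated.** Ratings at discontinuation visits are kept. So are ratings at scheduled visits, where the CGI-S-driven increases of protocol 10.2 take place.
- **That the bias in PANSS is known in size or direction.** A reduction for an adverse event need not coincide with a worse PANSS, and insufficient efficacy need not mean a score worse than the previous one.

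**Conclusion.** The point holds in two limited parts.

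1. SAP 6.4 departs from the LOCF definition in protocol 15.3.8.3. The departure is undeclared in SAP 8, differs from the SAP's own double-blind rule, and sits uneasily with SAP 7.9. It changes the result only for subjects whose last valid rating is an open-label unscheduled one. Their number is not given. Under the wider assumptions above, the long-term PANSS LOCF mean moves by 0.05 to 2.0 points, and it looks too favourable only if the omitted scores are worse. The primary conclusion does not depend on it.
2. DIEPSS scores collected before unscheduled reductions for extrapyramidal symptoms have no place in the DIEPSS tables. For those ratings the omission follows from the rules themselves and needs no assumption about frequency, apart from the unclear reach of the LOCF bar. The related adverse events are still reported.

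The absence of mapping for open-label unscheduled visits is not an error. Both parts deserve correction because the correction is small, not because the harm is large.

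**What to change.** 1. **SAP 6.4:** delete the sentence barring open-label unscheduled visits, so that LOCF is the final post-baseline value as in protocol 15.3.8.3. State which end-of-treatment LOCF this covers by region and group: Open-Week 28 or 52 for the open-label phase; On-treatment Week 34 or 58 for the 40 mg and 80 mg groups; On-treatment Week 28 or 52 for the placebo group. Reconcile the text with SAP 7.9. If the sponsor prefers to keep the exclusion, the change and its reason belong in SAP section 8.
2. **SAP 7.7.2:** add a descriptive summary of the worst post-baseline DIEPSS total score (overall severity excluded), including unscheduled visits, for the DSP-5423P treatment period in the DSP-5423P dosed population. SAP 7.7.5 and 7.7.7 already use unscheduled values in this way for laboratory values and QTc.

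No change to visit mapping is needed. Mapping only to missing visits would still leave out most ratings taken before a dose change, because the scheduled visit usually exists.

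Cost: SAP wording, minor reprogramming and one extra table from data already collected. Long-term summaries may look slightly less favourable.
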